3. STATISTICAL ANALYSES

The statistical analyses will be conducted in R (R Core Team, 2013) using the lme4 package (Bates, Mächler, Bolker, & Walker, 2015). Numeric dependent variables (tests scores, naming latency, dwell time) will be analyzed using linear mixed-effects models (LMM), and binary data (accuracy) will be analyzed using generalized linear mixed-effects models (GLMM) with a binomial link function.

The following fixed effects will be entered into the models:

- rTMS interventions (right frontal, right temporal),
- Assessment time (pre, intermediate, post),
- Interaction between rTMS protocol and assessment time.

Participants and items will be included in the models as random effects.

The lmerTest package (Kuznetsova, Brockhoff, & Christensen, 2017) in R will be used to calculate the *p* values (alpha level at .05).

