2. METHODS

Research Design

Randomized controlled trial

Population

People with aphasia aged between 18-80 whose native language is Turkish

Sample, Inclusion and Exclusion Criteria

20 participants

Inclusion Criteria:

- Right-handedness,
- Normal or corrected-to-normal vision and hearing,
- Aphasia following cerebrovascular accident,
- Cerebrovascular accident at least 6 months prior to enrolment in the study,
- Satisfying current TMS safety guidelines (Rossi et al., 2021, 2009), which are:
 - No previous history of epilepsy,
 - No implants (e.g., cochlear implant) or stimulators (e.g., deep brain stimulation) in the head which may interact with the magnetic field,
 - No use of central nervous system (CNS) active drugs that lower seizure threshold (as listed in the aforementioned guidelines)

Exclusion Criteria:

- Left-handedness, ambidexterity,
- Impaired and uncorrected vision or hearing,
- No aphasia symptoms following cerebrovascular accident,
- Time since cerebrovascular accident less than 6 months,
- Violating current TMS safety guidelines (Rossi et al., 2021, 2009). In other words:
 - Having a previous history of epilepsy,

- Having an implant (e.g., cochlear implant) or a stimulator (e.g., deep brain stimulation) in the head which may interact with the magnetic field,
- Taking central nervous system (CNS) active drugs that lower seizure threshold (as listed in the aforementioned guidelines)

rTMS Interventions

Intervention 1: Right frontal (inferior frontal gyrus) 1 Hz rTMS

Low-frequency (1 Hz) inhibitory rTMS will be administered to right inferior frontal gyrus with the following parameters:

- Frequency: 1 Hz
- Stimulation site: Right IFG (as determined using EEG 10-20 system)
- Intensity: 100% of motor threshold
- Dosage: 20 minutes per day
- Duration: 10 days over 2 weeks (no stimulation during weekends)

Intervention 2: Right temporal (posterior superior temporal gyrus) 1 Hz rTMS

Low-frequency (1 Hz) inhibitory rTMS will be administered to right posterior superior temporal gyrus with the following parameters:

- Frequency: 1 Hz
- Stimulation site: Right posterior superior temporal gyrus (as determined using EEG 10-20 system)
- Intensity: 100% of motor threshold
- Dosage: 20 minutes per day
- Duration: 10 days over 2 weeks (no stimulation during weekends)

Outcome Measurements

1. ADD Scores

Baseline and post-treatment scores obtained from the Turkish Aphasia Language Assessment Test (ADD)

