Time Frame: Immediately before and immediately after the intervention

2. Naming Scores

Naming performance (% accurately named pictures & naming latency for correctly named pictures) on the IPNP picture sets

Time Frame: Immediately before, during and immediately after the intervention

3. Eye movements

An eye tracking-while-listening paradigm will be used to determine proportions of dwell time on the correct picture (out of two alternatives) corresponding to auditorily presented Turkish sentences which vary in morphosyntactic complexity.

Time Frame: Immediately before and immediately after the intervention

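### Adjusting the ADD comparison for baseline ADD would be a cheap improvement: with one score per visit, the planned interaction is a valid raw-change test that fixes the baseline slope at 1

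*Combined protocol and SAP*

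**What the plan says.** Section 2 (Methods) describes a "Randomized controlled trial" of two stimulation sites with "20 participants". It gives no allocation ratio, power, effect size or SD. The first outcome is "Baseline and post-treatment scores obtained from the Turkish Aphasia Language Assessment Test (ADD"), and its timing is "Time Frame: Immediately before and immediately after the intervention". ADD therefore has two visits and no intermediate one.

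Section 3 (Statistical Analyses) says "Numeric dependent variables (tests scores, naming latency, dwell time) will be analyzed using linear mixed-effects models (LMM"). The fixed effects are the intervention, "Assessment time (pre, intermediate, post") and the "Interaction between rTMS protocol and assessment time". The baseline score thus enters as an outcome level, and no baseline covariate is listed for any outcome. The same section states "Participants and items will be included in the models as random effects". Neither section says whether ADD is analysed as one total, as subtests or as items.

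**The concern.** With 20 people, no severity limit among the entry criteria and no stratification described, some chance difference in baseline ADD between arms is likely, and readers will see it. A raw-change comparison subtracts the whole baseline gap, which is exactly right only if the slope of post on pre is 1. If the slope is below 1, the arm that started lower shows the larger relative change for that reason alone. If it is above 1, the direction reverses. A model that estimates the slope removes the linear effect of the baseline ADD gap, though not of gaps in other factors, and may be more precise. At stake are how the ADD result reads when a gap is visible, and possibly some power.

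**Working it through.** **The plan's own figure.** The sample size of 20 comes without power, effect size or SD, so it cannot be reproduced. For scale, 10 per arm gives 80% power at a standardised difference of (1.96 + 0.84) x sqrt(2/10), about 1.25 (normal approximation, two-sided 0.05).

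**Inputs.** From the documents: N = 20, two arms, two ADD visits, alpha 0.05. Assumed: 10 per arm, two-sided tests, normal scores, one ADD score per visit, complete pairs, pre-post correlation rho, and k = post SD / pre SD. Then b = rho x k.

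**Step 1: what the planned test is.** A mixed model with arm, time, their interaction and a participant intercept was fitted to simulated two-score data. In one dataset the interaction estimate was 2.844 with t = 1.2556, and the pooled t-test on change gave the same values. An lmerTest check gave |t| = 0.24436 on 18 df, p = 0.80971, again matching the t-test. The match in t requires complete pairs and a participant variance not estimated at zero.

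**Step 2: shift from a chance gap.** The SD of the baseline gap is sqrt(2/10) = 0.447 pre SD. A gap of that size shifts the raw-change estimate by (1 - b) x 0.447 pre SD:

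| k | rho 0.5 | 0.7 | 0.8 | 0.9 |
|---|---|---|---|---|
| 1.0 | 0.22 | 0.13 | 0.09 | 0.04 |
| 1.1 | 0.20 | 0.10 | 0.05 | 0.00 |
| 1.2 | 0.18 | 0.07 | 0.02 | -0.04 |

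In simulation, the regression of the raw-change estimate on the gap had slope -0.50 at b = 0.5 and -0.10 at b = 0.9. For the covariate-adjusted estimate it was about 0.

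**Step 3: type I error.** Overall it is about 5% for both analyses. At k = 1.0 and rho 0.5, 0.7, 0.8, 0.9, the raw-change test has 8.7, 7.4, 6.8 and 5.8% in the 32% of trials with a gap above one SD of the gap, and 3.3, 4.0, 4.3 and 4.6% in the other 68%. These average out: 0.32 x 8.7 + 0.68 x 3.3 is about 5.0. The adjusted analysis has 5.0-5.1% in both groups.

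**Step 4: precision, averaged over gaps.** Variance ratio (adjusted / raw change) = k^2 (1 - rho^2) / (1 + k^2 - 2 rho k) x (N - 3)/(N - 4), where the last factor is 17/16 at N = 20:

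| k | rho 0.5 | 0.7 | 0.8 | 0.9 | 0.95 |
|---|---|---|---|---|---|
| 0.8 | 0.61 | 0.67 | 0.68 | 0.65 | 0.55 |
| 0.9 | 0.71 | 0.80 | 0.84 | 0.86 | 0.84 |
| 1.0 | 0.80 | 0.90 | 0.96 | 1.01 | 1.04 |
| 1.1 | 0.87 | 0.98 | 1.03 | 1.06 | 1.04 |
| 1.2 | 0.92 | 1.03 | 1.06 | 1.04 | 0.93 |

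With equal SDs the ratio is (1 + rho)/2 x 17/16, so break-even is rho = 32/17 - 1 = 0.88. Where the planned test has 80% power, the adjusted analysis has 87.8, 83.6, 81.4, 79.4 and 78.4% along the k = 1.0 row. The lowest power in any simulated cell (k 0.8-1.2, rho 0.5-0.95) is 77.4%, a loss of 2.6 points. Allocations of 8/12 and 7/13 change the k = 1.0 powers by at most 0.2 points.

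**Step 5: the cost at b = 1.** Given the realised baseline t statistic, the variance is multiplied by 1 + t^2/(N - 2).

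- Averaged over gaps: 1/(N - 4) = 1/16 = 6.25% at N = 20, 1/12 = 8.3% at N = 16, and 1/10 = 10% at N = 14.
- At t = 1: 1/18 = 5.6%. At t = 2: 4/18 = 22%.
- In the 32% of trials with a gap above one SD: 15.8% on average. For a standard normal Z, the mean of Z^2 given |Z| > 1 is 2.525, and 2.525/16 = 0.158.

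**The case against.** The strongest reply is that nothing here is wrong. The planned test is unbiased over randomisations and holds its error rate, no passage contradicts another, and ADD is one of three outcomes with none named primary. All of that stands, so this is an improvement only.

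A second reply is that rho may be high: patients are at least 6 months post-stroke, severity is not restricted, and the retest follows a two-week course. That is an inference, since the documents give no value. If rho is about 0.9 with equal SDs, the variance ratio is 1.01 and a one-SD gap shifts the estimate by only 0.04 pre SD, so the change makes almost no difference.

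A third reply also stands. If the benefit is argued for trials with a visible gap, the cost must be priced there too. A reader might infer from 17/16 that the loss can never exceed about 6%. It can: the figure is an average over chance gaps for 20 complete pairs. At b = 1 and baseline t = 2, power falls from 80% to about 71%.

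Finally, the unit of analysis is open, because the plan places items in the models. In one simulated dataset with eight subtests as rows and complete data, the interaction still equalled the difference in mean change, so the shift persists. But its standard error was 0.121 on 291 df, against 0.228 on 18 df for the t-test on change. The precision and power figures above do not carry over to that analysis.

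**Conclusion.** The point holds for ADD, as a low-cost improvement, on the condition of one score per visit and complete pairs. The planned interaction then fixes the baseline slope at 1, and its estimate moves by (1 - b) times a chance baseline gap. Baseline adjustment removes that movement.

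The precision effect depends on two quantities that the documents do not give. Over rho 0.5-0.95, variance falls 32-45% at k = 0.8 and 14-29% at k = 0.9. With equal SDs it ranges from a 20% fall to a 4% rise, and at k of 1.1 to 1.2 from a 13% fall to a 6% rise.

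A reader might infer that the planned test is biased or inflates type I error. It does neither over randomisations; the error rate departs from 5% only when trials are sorted by the size of the gap. A reader might also infer that adjustment always gains precision, or that the point extends to naming and eye movements. The first is false in part of the range shown, and the second was not examined.

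**What to change.** For ADD only, add to section 3:

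> Post-treatment ADD score will be analysed by a linear model with rTMS protocol and baseline ADD score as a covariate; the adjusted difference between protocols is reported with its 95% CI.

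State whether ADD is a total or a set of subtests. If subtests, use each subtest's own baseline and say how the several tests will be handled.

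The change needs no new data. It uses one degree of freedom (18 to 17), drops anyone lacking either ADD score, and carries the variance cost set out above.

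A mixed model with arm means constrained to be equal before treatment would retain people with one missing score, but only as an optional sensitivity analysis. With a participant intercept and Satterthwaite df, its simulated type I error was 5.5-6.1% with equal SDs, up to 7.7% with a post SD 20% larger, and down to 3.4% with one 20% smaller. The covariate-adjusted model stayed at 4.8-5.3% in the same runs.

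### The models name no participant-by-time random term, so item-level protocol-by-time tests can exceed the stated .05 when true change differs between people

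*Combined protocol and SAP*

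**What the plan says.** Section 3 (Statistical Analyses) enters protocol, assessment time and their interaction as fixed effects. The term that answers the trial's question is listed as "Interaction between rTMS protocol and assessment time". Numeric outcomes go into linear mixed models, and "binary data (accuracy) will be analyzed using generalized linear mixed-effects models (GLMM) with a binomial link function". The random part is given in full by "Participants and items will be included in the models as random effects". P values come from lmerTest with "alpha level at .05". No section mentions a random slope, a participant-by-time or participant-by-session term, or a rule for choosing the structure.

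Under Outcome Measurements in section 2, naming is defined as "Naming performance (% accurately named pictures & naming latency for correctly named pictures) on the IPNP picture sets", with "Time Frame: Immediately before, during and immediately after the intervention", so it has three assessments. For the eye-movement outcome, "An eye tracking-while-listening paradigm will be used to determine proportions of dwell time on the correct picture", before and after treatment only. These outcomes yield many trials per participant per session, and a random item effect implies trial-by-trial modelling. The design is described only as "Randomized controlled trial", with 20 participants and no allocation ratio.

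**The concern.** Protocol is assigned to people. With parallel arms, the independent pieces of evidence about a difference in change are therefore the 20 individual changes, not the hundreds or thousands of trials. A participant intercept absorbs differences in level but assumes that everyone in an arm changes by the same amount. Any real variation in change is left in the residual, or ignored in the binomial case. The model then treats it as if it averaged out over trials, when it averages out only over people. Item intercepts do not help, because the omitted variance belongs to participants.

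The standard error of the interaction is then too small. One protocol could be declared better because a few people in that arm happened to improve more. Because the sentence permits more than one structure, the choice could also be made after the data are seen.

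**Working it through.** **Inputs.** From the documents: 20 participants, alpha .05, the protocol-by-time interaction as the tested term, three naming assessments and two eye-movement assessments. Assumed, because the documents do not give them: a two-sided test; parallel arms of 10; K items per session; s, the SD of true pre-to-post change in residual SDs (in logits for accuracy). No mean protocol effect was present in any calculation, so every rejection is a false positive.

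**1. Linear model, two visits (for example dwell time).** With residual variance σ² and n₁, n₂ people per arm:

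- variance the intercepts-only model assumes: (1/n₁ + 1/n₂)(2σ²/K)
- true variance: (1/n₁ + 1/n₂)(2σ²/K + s²σ²)
- ratio: 1 + K·s²/2, which does not depend on the number per arm
- actual error rate: 2[1 − Φ(1.96/√(1 + K·s²/2))]

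The plan's own figure comes first: at s = 0 the ratio is 1 and the formula returns .050. For K = 50, s = 0.2 the ratio is 1 + 50 × 0.04/2 = 2, and 1.96/√2 = 1.386, which gives .166.

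The simulated columns come from a balanced mean-square simulation with 400,000 draws per row. The last column is a model with a participant-by-session intercept, kept even when that variance is estimated as zero.

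| K | s | Ratio | SE ratio | Formula | Simulated, intercepts only | Simulated, participant-by-session |
|---|---|---|---|---|---|---|
| any | 0 | 1.00 | 1.00 | 5.0% | 5.0% | 3.7% |
| 20 | 0.1 | 1.10 | 1.05 | 6.2% | 6.1% | 4.0% |
| 50 | 0.1 | 1.25 | 1.12 | 8.0% | 7.9% | 4.4% |
| 50 | 0.2 | 2.00 | 1.41 | 16.6% | 16.4% | 5.0% |
| 100 | 0.2 | 3.00 | 1.73 | 25.8% | 25.6% | 5.0% |

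The rate reaches 10% when √(1 + K·s²/2) = 1.96/1.645, that is K·s²/2 = 0.42 and s = √(0.84/K). This is about 0.205 for K = 20, 0.13 for K = 50 and 0.09 for K = 100.

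**2. Naming latency, three visits.** lmerTest fits with the 2-df Satterthwaite F test. Only correct trials are used, with each person's accuracy drawn between 0.3 and 0.8. There were 250 runs per row (Monte Carlo SE 1.2 to 2.2 points for intercepts only). The fixed-order rule is the one set out in the proposed change.

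| K | s | Form of change | Intercepts only | Fixed-order rule | Share reaching step 2 |
|---|---|---|---|---|---|
| 50 | 0 | none | 5.2% | 3.6% | 76% |
| 20 | 0.1 | linear | 4.0% | 2.8% | 75% |
| 50 | 0.2 | linear | 10.4% | 3.2% | 57% |
| 50 | 0.2 | session-specific | 14.4% | 5.2% | 33% |
| 100 | 0.2 | linear | 14.4% | 5.6% | 50% |

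**3. Naming accuracy, two visits.** glmer with its default Laplace fit, participant and item intercept SDs of 1 logit, Wald z test, 580 runs per row (Monte Carlo SE 0.9 to 1.5 points).

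| K | Change SD (logit) | Intercepts only | Participant-by-session | Participant-level t test |
|---|---|---|---|---|
| 20 | 0 | 5.3% | 4.8% | 5.3% |
| 20 | 0.3 | 6.4% | 5.3% | 4.1% |
| 20 | 0.5 | 12.2% | 8.8% | 5.3% |
| 50 | 0.5 | 16.2% | 5.3% | 3.4% |

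A further 272 glmer runs at K = 20, 0.5 logit gave 10.3% with intercepts only, 7.7% with the participant-by-session term and 6.6% with a random slope.

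The ADD score, if analysed as one value per session at two times, is not affected: variation in change is then already in the residual.

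**The case against.** The strongest reply is that this is an omission, not a demonstrated error. The sentence never says intercepts and does not exclude slopes, so the excess follows on one reading only. That is true. But the sentence is all an analyst would have, and its plain reading gives the invalid test.

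Second, the size cannot be fixed from the documents. The scenarios run from no visible excess (latency at K = 20, s = 0.1; accuracy at K = 20, 0.3 logit, within simulation error of 5%) to 26%, and none can be called likely for this trial. The latency rows are also imprecise: 10.4% from 250 runs has a 95% Monte Carlo interval of about 6.6% to 14.2%. This stands as a limit on the magnitude, not on the direction.

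Third, the remedy is imperfect. For accuracy at K = 20, 0.5 logit, the participant-by-session model still rejected 8.8% (about 6.5% to 11.1%), while the participant-level t test held at 5.3%. The fallback order was fitted in full only for latency, with singularity as the only trigger, so convergence failure was not tested. Dropping slope correlations also depends on how time is coded. The standard-error ratios belong to the balanced two-visit linear model and do not carry over directly to the other outcomes. These points qualify the fix. They do not make the intercepts-only test valid.

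**Conclusion.** The concern holds. On its plain reading, the plan tests protocol-by-time on item-level outcomes against the wrong source of variation, and the rate can exceed .05 whenever true change differs between participants. If change does not differ, the rate stays at 5%. In the scenarios examined, intercepts-only rates were about 5% to 26% for two-visit linear models, 4% to 14% for three-visit latency and 5% to 16% for accuracy.

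These figures rest on assumed parallel arms of 10, assumed item counts and assumed variation in change. The direction is secure if change varies, but the size for this trial is unknown. This should be fixed before analysis. Confidence is medium, because slopes may have been intended and the quantities that set the size are missing.

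**What to change.** Replace the random-effects sentence in section 3 with:

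> For item-level outcomes (naming accuracy, naming latency, dwell time) the models will include random intercepts for participants and items and a by-participant random slope for assessment time (categorical). If this model does not converge or is singular, the following are tried in this fixed order: (1) drop the slope correlations; (2) replace the slope with a participant-by-session random intercept. The model at step 2 is kept even if its participant-by-session variance is estimated as zero. Only if step 2 does not converge are protocols compared on each participant's mean pre-to-post change with a two-sample t test (df = participants analysed minus 2).

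This wording assumes parallel arms, which section 2 should state. The coding of time used at step 1 should be stated too. For naming accuracy, a participant-level t test on change in percentage correct could be reported alongside the model, since the Wald test may still run above 5% with few items.

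**Cost.** A short change to the SAP and some convergence work: the rule reached step 2 in 33% to 76% of the simulated latency datasets. Intervals widen. In the two-visit linear model the standard error rises by about 5% (K = 20, s = 0.1), 12% (K = 50, s = 0.1), 41% (K = 50, s = 0.2) or 73% (K = 100, s = 0.2). If people do not differ in change, the test is slightly conservative, at about 3.7%. That arises because the participant-by-session variance is estimated as zero in 54% of such datasets and above zero in the rest.

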1. PURPOSE

The purpose of the study is to compare effectiveness of two repetitive transcranial magnetic stimulation (rTMS) protocols in rehabilitation of aphasia:

1. Inhibitory, low-frequency stimulation of right inferior frontal gyrus,
2. Inhibitory, low-frequency stimulation of right posterior superior temporal gyrus.

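### No primary outcome or deciding contrast is named and every test is run at .05, so across four measures the chance of a false protocol difference is about 10% to 18.5%

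*Combined protocol and SAP*

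**What the plan says.** Section 1 gives a single comparative aim: "The purpose of the study is to compare effectiveness of two repetitive transcranial magnetic stimulation (rTMS) protocols in rehabilitation of aphasia".

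Section 2 (Outcome Measurements) lists three numbered outcomes that hold four measures:

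- **ADD:** "Baseline and post-treatment scores obtained from the Turkish Aphasia Language Assessment Test (ADD").
- **Naming:** "Naming performance (% accurately named pictures & naming latency for correctly named pictures) on the IPNP picture sets". This is two measures, and their time frame is "Immediately before, during and immediately after the intervention".
- **Eye movements:** the share of looking time on the matching picture. Like ADD, this is taken only before and after treatment.

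Section 3 models each measure separately. "Numeric dependent variables (tests scores, naming latency, dwell time") go into linear mixed models, and accuracy goes into a binomial mixed model. Every model carries a protocol effect, a time effect and the "Interaction between rTMS protocol and assessment time". The only decision rule is that the lmerTest package "in R will be used to calculate the *p* values (alpha level at .05").

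The text supplied for review does not label any outcome primary or secondary. It does not say which model term answers the question, how mixed results across measures will be read, or that the trial is exploratory.

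**The concern.** A single question is tested several times at the full .05, with no rule for combining the answers. A p value below .05 on any one of the four measures could be presented as showing that one protocol is better, and the chance that at least one such result is false exceeds 5%.

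Two further choices are open.

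- **The term.** Only the protocol-by-time interaction compares change between protocols, yet it is listed beside two main effects with no indication of which decides. The protocol main effect depends on factor coding, which is not stated. With the pre assessment as reference it is the pre-treatment difference; with sum coding it is an average that includes the pre score. Neither compares change.
- **The time point.** For the two naming measures the interaction has an intermediate and a post contrast, and the plan does not say which counts. ADD and eye movements have one contrast each, so this choice is open for naming only.

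None of these choices can be made credibly once the data have been seen.

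**Working it through.** The plan gives no familywise error rate, power or sample-size derivation, so there is no stated figure to reproduce.

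**Inputs from the documents.** Per-test level .05 (section 3); four measures (section 2); one protocol-by-time interaction per model (section 3); three naming assessments and two for ADD and eye movements (section 2); 20 participants (section 2).

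**Assumptions.** Two-sided tests; 10 per arm (allocation is not stated); each interaction test holds exactly 5%; equal correlation between measures, shown as a range; ADD counted as one score, although section 3 speaks of test scores in the plural and section 2 does not say which ADD score is analysed.

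**Step 1: independent measures.** P(at least one false difference) = 1 − (1 − 0.05)^4 = 1 − 0.8145 = 0.1855, or 18.5%.

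**Step 2: correlated measures.** 200,000 null trials per setting were simulated with 10 per arm and four equally correlated normal change scores, using two-sample t tests on 18 df. These tests stand in for the post-minus-pre interaction; they are not the planned mixed models. As a check, the large-sample version was integrated numerically (equicorrelated normal, critical value 1.96).

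| Correlation | Simulation, t tests | Normal integration |
|---|---|---|
| 0 | 18.5% | 18.5% |
| 0.3 | 17.6% | 17.4% |
| 0.5 | 15.9% | 15.6% |
| 0.7 | 13.5% | 13.0% |
| 0.9 | 9.6% | 9.4% |

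If the two naming measures are instead tested with 2-df interactions over three time points, the rate is 16.2% at 0.5 and 11.0% at 0.9.

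**Step 3: both naming contrasts tested separately.** This gives 4 + 2 = 6 tests. Intermediate and post changes on one measure share a baseline, so a correlation of 0.5 between them was used (compound symmetry). The rate is 25.4%, 19.6% and 14.9% at between-outcome correlations of 0, 0.7 and 0.9. Repeat simulations agreed with the figures in steps 2 and 3 to within about 0.4 percentage points.

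**Step 4: effect of the remedies.**

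- Holm across all four: the first step is .05/4 = .0125. At independence the rate is 1 − 0.9875^4 = 4.9%. Simulation gives 3.8% at 0.7 and 2.7% at 0.9.
- One primary at .05 plus Holm across the other three: the first secondary step is .05/3 = .0167. At independence the rate over both families is 1 − 0.95 × (1 − .05/3)^3 = 1 − 0.95 × 0.9508 = 9.7%.

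**Step 5: power cost.** Noncentral t, 18 df, 10 per arm. A difference in change of 1.325 SD has 80% power at .05, 63% at .0167 and 58% at .0125.

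**The case against.** The strongest reply is that this is a small trial whose measures cover different abilities: a test battery, picture naming and sentence comprehension. They could be read as separate questions, and separate questions need no joint error control. The plan does not claim such control and does not say that success on any one measure suffices. Listing main effects beside an interaction is ordinary model specification, and a comparative aim in a randomised design points to the interaction anyway. This softens the point but does not remove it. Section 1 poses one question about effectiveness, section 3 sets a significance threshold, and nothing declares the trial exploratory or links each measure to its own conclusion.

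The percentages are also open to challenge. The correlation of 0.9 has no source in the documents and marks the favourable end of an illustration, not a bound. The 5% premise may fail: section 3 says only that participants and items are random effects, and a model with random intercepts alone, fitted to item-level data, need not hold its level. These objections stand as limits on the precision of the figures. They do not affect the finding that the hierarchy is missing.

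Finally, a primary test plus a separate Holm family leaves 9.7% over both families at independence, close to the rate given for four unadjusted tests at correlation 0.9. That is true. The difference is that the conclusion would then rest on one pre-named test at 5%.

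**Conclusion.** The concern holds. As written, the plan lets the single comparative question be answered by any of four tests at .05. The chance of at least one false protocol difference is 18.5% for independent measures and about 10% at an assumed correlation of 0.9, roughly two to four times the per-test level. It reaches 25.4%, about five times, if both naming contrasts are tested and outcomes are uncorrelated. These figures assume that each test holds 5%; the simulated ones also assume 10 per arm and equal between-outcome correlations. Analysing several ADD scores would add further tests.

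The missing primary outcome, naming contrast and multiplicity rule are plain from the text; the percentages illustrate the consequence. This should be corrected before data are seen. It does not prevent the trial from running.

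**What to change.** Add to section 3, before any outcome data are examined, wording to this effect:

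> The primary test is the protocol-by-time contrast for post minus pre on [one named outcome], two-sided at .05, and the conclusion about which protocol is more effective rests on it. The same contrast on the other three measures is secondary, with Holm adjustment across the three.

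The sponsor chooses the outcome. ADD is listed first and is an obvious candidate, although list order is not a statement of priority. If ADD is used, say which ADD score.

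There are two acceptable alternatives. If no single primary is wanted, apply Holm across all four post-minus-pre contrasts. If the trial is meant to be exploratory, say so, report estimates with 95% confidence intervals, and do not declare a better protocol.

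In every case, report the intermediate naming contrasts and the protocol and time main effects as estimates with 95% confidence intervals. They should not be used as evidence that either protocol works, because there is no untreated arm.

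**Cost.** A few sentences. The primary test keeps the full .05. At the effect size giving 80% power at .05, a secondary measure has 63% at its first Holm step, or 58% if Holm covers all four; later steps are less strict. The primary-plus-Holm scheme controls error at 5% within each family, not over both. If 5% overall is wanted, use Holm across all four.
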